6. INVESTIGATIONAL PLAN

6.1 Overall Study Design and Plan – Description

This is a Phase 2 multi-center, open label study in 29 FLC patients. Patients will receive a daily oral dose (fasting) of ENMD-2076 as a single treatment agent. The starting dose will be based on body surface area. If adverse events, two dose reductions at the discretion of the investigator will be allowed for each patient. If adverse events resolve, the dose can be increased in 50 mg increments as tolerated. Dosing interruptions/delays will be allowed at the discretion of the investigator for recovery from adverse events or inter-current illness, particularly if the patient is benefiting from ENMD-2076 treatment. After a treatment interruption for adverse events, treatment can be resumed at a lower dose and increased in 50 mg increments as tolerated. Patients may be treated until disease progression or unacceptable toxicity.

Once a potential patient has been identified and signed the informed consent form, the screening and baseline visit procedures will be completed. Following the baseline visits, patients meeting all study entry criteria will start Cycle 1 and get their first dose of ENMD-2076. Each cycle of treatment consists of a 4-week treatment period. Patients who complete the initial cycle of therapy (4 weeks of treatment) without evidence of significant toxicity or clinical evidence of progressive disease may receive additional 4-week cycles of treatment.

Patients who discontinue therapy for any reason other than progression will continue to receive imaging until progression or death. All recruited subjects will be followed for safety and overall survival.

6.2 Discussion of Study Design and Choice of Control Group(s)

The primary objective of this trial is to determine the overall response rate using RECIST v 1.1 criteria when patients with advanced fibrolamellar carcinoma (FLC) are treated with daily oral ENMD-2076. Since there is no standard therapy approved to treat patients with FLC, it is appropriate for this evaluation to be conducted as a single arm, open label, non-controlled study.

The interim analysis with the initial 16 patients is to establish proof of concept before expanding the treatment to the full planned population of patients.

6.3 Selection of Study Population

6.3.1 Inclusion Criteria

The subjects must meet the following inclusion criteria:

1. Histologically or cytologically confirmed advanced not amenable to curative resection fibrolamellar carcinoma.
 - a) This review will be conducted by a pathologist at the participating site to confirm the diagnosis. If there is a discrepancy, a review of a different archived specimen if available (heterogeneity is common) and/or identify a liver pathologist at another site who can provide independent review.
 - b) Archived specimens will be collected for subsequent immunohistochemistry, genomic analysis, and possibly other research.
2. All forms of prior local therapy are allowed as long as patients have either a target lesion which has not been treated with local therapy and/or the target lesion(s) within the field of the local-regional therapy that has shown an increase of $\geq 20\%$ in size. Local-regional therapy must be completed at least 4 weeks prior to the baseline CT scan.
3. Patients with prior systemic regimens are allowed,. There is no limitation to the number of previous systemic regimens but must have recovered from any toxicity attributable to prior therapy.
4. Are at least 4 weeks from major surgery or systemic therapy and recovered.
5. At least one measurable lesion by RECIST 1.1.
6. Male or non-pregnant, non-breastfeeding female at least 18 years of age. Patients aged at 12~18 years may be recruited but only at the site principle investigator's request and subject to IRB approval.
7. Have clinically acceptable laboratory screening results within certain limits specified below:
 - ∞ AST and ALT ≤ 5 times upper limit of normal (ULN)

- ∞ Total bilirubin $\leq 3.0 \times$ ULN
- ∞ Creatinine $\leq 1.5 \times$ ULN or Cr Cl $> 60 \text{ cc/min}$
- ∞ Absolute neutrophil count $\geq 1500 \text{ cells/mm}^3$
- ∞ Platelets $\geq 50,000/\text{mm}^3$

8. Have an ECOG performance status of 0-2 for ≥ 16 years of age and a Lansky performance status of 70-100 for < 16 years of age.
9. Women and men of child producing potential must agree to use effective contraceptive methods prior to study entry, during study participation, and for at least 30 days after the last administration of study medication. A serum pregnancy test within 72 hours prior to the initiation of therapy will be required for women of childbearing potential.
10. Have the ability to understand the requirements of the study, provide written informed consent or assent which includes authorization for release of protected health information, abide by the study restrictions, and agree to return for the required assessments.

6.3.2 Exclusion Criteria

The presence of any of the following excludes a subject from study enrolment:

1. Have active, acute, or chronic clinically significant infections, chronic hepatitis or HIV, thromboembolic or hemorrhagic event with concomitant treatment, in therapeutic doses, with anticoagulants such as warfarin or warfarin-related agents, heparin, thrombin or Factor Xa inhibitors, or antiplatelet agents (eg, clopidogrel). Low dose aspirin ($\leq 81 \text{ mg/day}$), low-dose warfarin ($\leq 1 \text{ mg/day}$), and prophylactic low molecular weight heparin (LMWH) are permitted.
2. Have uncontrolled hypertension (systolic blood pressure greater than 150 or diastolic blood pressure greater than 100) or history of congestive heart failure (AHA Grade 2 or higher).
3. Have active cardiovascular disease.
4. QTc interval corrected for heart rate of greater than 470 msec in adults and 450 msec in pediatrics (< 18 years).
5. Have additional uncontrolled serious medical or psychiatric illness that in the point of view of the investigator can render the patient unable to receive therapy or make it unsafe to receive therapy.
6. Require treatment with any of the exclusionary medications listed in [Appendix D](#).
7. Known untreated or unstable CNS metastatic disease.
8. Have persistent 2+ protein by urinalysis (patients with 2+ proteinuria that have a spot protein:creatinine ratio of less than 0.3 may be enrolled) or a history of nephrotic syndrome.

9. Subjects with history of another primary cancer, with the exception of: a) curatively resected non-melanoma skin cancer; b) curatively treated cervical carcinoma in situ; or c) other primary solid tumor with no known active disease present in the opinion of the investigator will not affect patient outcome in the setting of current FLC diagnosis.

6.3.3 Removal of Subjects from Therapy or Assessment

The Investigator or the Sponsor may discontinue individual patients from the study at any time. Patients will be encouraged to complete the study; however, they may voluntarily withdraw at any time. The Investigator or designee will document the reason for discontinuation. Patients who went off therapy without evidence of disease progression will have CT scans every two months until disease progression or death.

A patient will be withdrawn from treatment for the following reasons:

∞ Significant adverse event:

If a patient suffers an AE that, in the judgment of the Investigator, the Sponsor, or the Medical Monitor, presents an unacceptable consequence or risk to the patient, whether or not the AE is considered related to study medication, the patient will be withdrawn from treatment.

∞ Pregnancy

If a female patient becomes pregnant at any time during the study, she will be discontinued from further participation and treatment. See [Section 8.3.7](#) for further information on recording and follow-up of pregnancies.

∞ Disease progression:

Progression by RECIST v. 1.1 criteria, unless in the judgement of the investigator the patient has derived benefit from the treatment.

∞ Consent withdrawn:

The patient chooses to terminate participation in the study.

∞ Noncompliance

Failure to receive or refusal of study medication.

Failure to comply with protocol requirements. The patient has a serious deviation from the protocol that would compromise the integrity of the study data. All occurrences of noncompliance must be documented on the appropriate CRF pages.

6.3.4 Replacement Policy

Withdrawn patients will not be replaced.

7. STUDY PRODUCT

[figure not shown]
7.1 Study Medication Supply

CASI Pharmaceuticals will supply all ENMD-2076 clinical trial material (CTM), including study medication and supplies, to the study site. CTM will be shipped to the study site only after receipt of required documents in accordance with applicable regulatory requirements and standard operating procedures. The Principal Investigator, or authorized study personnel, upon receipt of the study medication supplies, will conduct an inventory and acknowledge receipt to CASI Pharmaceuticals, or designee.

7.2 Description of Study Product

ENMD-2076 is an off-white to yellow, odorless, crystalline solid manufactured by DSM Pharma Chemicals (DSM). The structural formula is illustrated in Figure 1.

Figure 1 Structural Formula of ENMD-2076

ENMD-2076 is provided as hard gelatin capsules and is intended for oral administration. The active pharmaceutical ingredient is chemically synthesized 2-(2-phenylvinyl)-4-[4-methylpiperazin-1-yl]-6-(5-methyl-2H-pyrazol-3-yl-amino)-pyrimidine L(+) tartrate salt with an empirical formula of $C_{25}H_{31}O_6N_7 \cdot (2.5 H_2O)$ and molecular weight of 570.59.

ENMD-2076 will also be supplied as 50 mg formulated pharmaceutical product filled into hard gelatin capsules, size 1 white body capsule. The composition of this formulated product is a granulated mixture comprised as noted in the Table 1 below. All components of the formulation are common excipients used in formulating a wide range of oral drug products.

Table 1: Composition of the Formulation for ENMD-2076 Capsules

Component	% in Final Mixture
Intrgranular Component	
ENMD-2076	50%
MCC Avicel PH 101	30%

Methocel E5LV	3%
Sodium croscarmelose	3%
Cab-o-Sil (colloidal silicon dioxide)	0.5%
Mg Stearate (non-bovine #5712)	0.5%
Extrgranular Component	
MCC Avicel PH 101	10%
Sodium croscarmelose	2%
Cab-o-Sil (colloidal silicon dioxide)	0.5%
Mg Stearate (non-bovine #5712)	0.5%
Total	100%

7.3 Description of Comparator Product

Not applicable.

7.4 Dosing

The planned starting dose for this study is approximately 160 mg/(m²) of body surface area and is dosed in 50 mg increments per the following chart.

Body Surface Area (m ²)	Daily Dose
< 1.00	150 mg
1.00 - < 1.40	200 mg
≥ 1.40	250 mg

The Investigator will provide specific instructions to the patient regarding self-administration of each dose. All patients will be instructed to refrain from eating for one hour before and one hour following all doses.

If adverse events occur from treatment, two dose reductions at the discretion of the investigator will be allowed for each patient. If adverse events resolve, the dose can be increased in 50 mg increments as tolerated. Dosing interruptions/delays will be allowed at the discretion of the investigator for recovery from adverse events or inter-current illness, particularly if the patient is benefiting from therapy with ENMD-2076. After a treatment interruption for adverse events, treatment can be resumed at a lower dose and increased in 50 mg increments as tolerated.

Dose Adjustment Guideline for ENMD2076-related Toxicity	Recommended Action
Persistent (i.e. lasting more than 2 weeks despite optimal medical intervention) OR Grade 2 toxicity that is deemed intolerable OR Grade ≥3 toxicity	∞ Hold dose until toxicity resolves to Grade ≤1 or baseline (maximum 14 days). ∞ If the patient is benefiting from treatment but toxicity does not resolve to Grade ≤1 or baseline within 14 days of discontinuation of study drug, then study drug treatment

	
may be delayed for an additional week. If toxicity persists despite the additional week off drug, then study drug will be discontinued permanently.
 
∞ If the toxicity resolves to Grade ≤ 1 or baseline within 14-21 days, restart drug administration as shown below.
First Reduction	
∞ Allow toxicity to resolve to Grade ≤ 1 or baseline, then restart dosing at dose level -1, 200 mg/day
Second Occurrence	
∞ Hold dose until toxicity resolves to \leq Grade 1 or baseline (maximum 14 days).∞ If the patient is benefiting from treatment but toxicity does not resolve to \leq Grade 1 or baseline within 14 days of discontinuation of study drug, then study drug treatment may be delayed for an additional week. If toxicity persists despite additional week off drug, then study drug will be discontinued permanently.∞ If the toxicity resolves to \leq Grade 1 or baseline within 14-21 days then restart dosing at a dose level -2 (150mg/day)
Third Occurrence	
∞ Discontinue study medication.∞ If patient is benefiting from therapy, discuss with PI.

Each cycle of treatment consists of a 4-week treatment period. Patients who complete the initial cycle of therapy (4 weeks of treatment) without evidence of significant toxicity or clinical evidence of progressive disease may receive additional 4-week cycles of treatment.

If any individual patient develops $\geq 2+$ proteinuria on qualitative assessment of protein on urinalysis, then a spot urine protein:creatinine ratio will be obtained, and a 24-hour urine collection will be obtained for quantification. If the spot protein:creatinine ratio remains equal to or below 1, then patients may continue to receive study drug until the 24-hour urine collection is complete (no longer than one week is allowed). If 24-hour urine shows greater than 3.5 g protein/24 hours then study drug will be held until the a repeat study shows a 24-hour urine below 3.5g.

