9. Subjects with history of another primary cancer, with the exception of: a) curatively resected non-melanoma skin cancer; b) curatively treated cervical carcinoma in situ; or c) other primary solid tumor with no known active disease present in the opinion of the investigator will not affect patient outcome in the setting of current FLC diagnosis.

TEST PRODUCT(S), DOSE AND MODE OF ADMINISTRATION: ENMD-2076 is provided as hard gelatin capsules containing 50 mg of drug.

Patients will receive a daily oral dose (fasting) of ENMD-2076 of 150, 200 or 250 mg/day based on body surface area.

DURATION OF TREATMENT: Following the Screening and Baseline Period (Day -28 to 1) each treatment cycle will consist of a 4-week Treatment Period (Cycle 1 to Cycle 6+). Patients will be treated until disease progression, unacceptable toxicity or death.

DISCONTINUATION FROM TREATMENT:

The Investigator or the Sponsor may discontinue individual patients from the study at any time. Patients will be encouraged to complete the study; however, they may voluntarily withdraw at any time. The Investigator or designee will document the reason for discontinuation. Patients who went off therapy without evidence of disease progression will have CT scans every two months until disease progression or death.

A patient will be withdrawn from treatment for the following reasons:

- ∞ Significant adverse event
- ∞ Pregnancy
- ∞ Disease progression
- ∞ Consent withdrawn
- ∞ Noncompliance

PRIMARY EFFICACY ENDPOINT:

Overall response rate based on RECIST v 1.1 criteria will be used to evaluate response every two months after first study drug administration. Patients who go off therapy without evidence of disease progression will have CT scans every two months until progression.

SECONDARY EFFICACY ENDPOINTS:

- ∞ Progression-free survival rate at 6 months (PFS6).
- ∞ The median PFS or TTP as based on RECIST 1.1 and measured by time from first study drug administration

until progression or death.

- ∞ The median overall survival as measured by time from first study drug administration to death or study completion.
- ∞ Safety data will be collected from time of informed consent through study completion /withdrawal up to 30 days after the last dose of study medication by each subject.

SAFETY ENDPOINTS:

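### The toxicity dose ladder (200, then 150 mg/day) works only for patients who start at 250 mg; read literally it gives a 200 mg starter no first reduction and a 150 mg starter an increase

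*Combined protocol and SAP*

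**What the plan says.** The synopsis gives three possible starting doses: "Patients will receive a daily oral dose (fasting) of ENMD-2076 of 150, 200 or 250 mg/day based on body surface area". Section 7.4 gives the basis, "The planned starting dose for this study is approximately 160 mg/(m²) of body surface area", and a chart: 150 mg below 1.00 m², 200 mg from 1.00 to below 1.40 m², and 250 mg at 1.40 m² or more.

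The narrative in 7.4 then says that, if adverse events occur, "two dose reductions at the discretion of the investigator will be allowed for each patient". It adds: "After a treatment interruption for adverse events, treatment can be resumed at a lower dose and increased in 50 mg increments as tolerated". The synopsis and section 6.1 say the same in nearly the same words.

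The table that follows is headed "Dose Adjustment Guideline for ENMD2076-related Toxicity". It applies to drug-related toxicity that is Grade 3 or higher, intolerable Grade 2, or persistent. Dosing is held until recovery. In the row for the first reduction the instruction is "then restart dosing at dose level -1, 200 mg/day". In the row for the second occurrence it is "restart dosing at a dose level -2 (150mg/day". At the third occurrence the drug is stopped, with a discussion with the PI if the patient is benefiting. No row mentions BSA or starting dose.

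**The concern.** The starting dose varies by patient, but the reduced doses are fixed amounts in mg. A fixed ladder of 200 then 150 mg/day is a reduction at both steps only for someone who began at 250 mg. In the two lower tiers, the table conflicts with the narrative directly above it.

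What is at stake is patient safety and uniform handling across sites. The patients concerned have a BSA below 1.40 m², have just recovered from a qualifying toxicity, and are restarting. Smaller patients are foreseen: section 6.3.1 says "Patients aged at 12~18 years may be recruited but only at the site principle investigator's request and subject to IRB approval", and adolescents may fall in the lower tiers. A lower-tier patient could also reach the stopping rule at the third occurrence without having had the two reductions that the narrative allows.

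**Working it through.** **Inputs, all from section 7.4:** starting doses 150, 200 and 250 mg/day; level -1 = 200 mg/day; level -2 = 150 mg/day; planned starting dose about 160 mg/m². The capsule strength of 50 mg is in the synopsis and section 7.2.

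**Step 1. Which starting dose does the ladder fit?** In 50 mg steps, 250 - 50 = 200 and 250 - 100 = 150. The printed ladder is reproduced exactly from a 250 mg start, and from no other.

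**Step 2. Change from the starting dose**, (ladder dose - starting dose) / starting dose:

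| Start | Level -1 (200 mg) | Level -2 (150 mg) |
|---|---|---|
| 250 mg | -50/250 = -20% | -100/250 = -40% |
| 200 mg | 0/200 = 0% | -50/200 = -25% |
| 150 mg | +50/150 = +33% | 0/150 = 0% |

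Three of the six cells are not below the starting dose. The 250 mg tier gets two true reductions, the 200 mg tier one, and the 150 mg tier none below where it started.

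**Step 3. Change from the dose at which the toxicity occurred**, assuming no re-escalation in between:

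- 250 mg tier: -20%, then 150 against 200 = -25%.
- 200 mg tier: 0%, then -25%.
- 150 mg tier: +33%, then 150 against 200 = -25%, which only returns the patient to the dose of the first toxicity.

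**Step 4. Dose per m² in the lowest tier.** A restart at 200 mg with BSA below 1.00 m² gives more than 200/1.00 = 200 mg/m². Since 200/160 = 1.25, that is more than 25% above the planned level. The documents give no BSA values, so the following are illustrations:

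| Assumed BSA | Start, 150 mg | Restart, 200 mg | Restart against 160 mg/m² |
|---|---|---|---|
| 0.99 m² | 152 mg/m² | 202 mg/m² | +26% |
| 0.90 m² | 167 mg/m² | 222 mg/m² | +39% |
| 0.80 m² | 188 mg/m² | 250 mg/m² | +56% |

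The last column mixes two effects: the rounding of the starting chart and the ladder. The ladder alone contributes +33% at every BSA in this tier. For comparison, the chart itself starts a patient of exactly 1.00 m² on 200 mg, which is 200 mg/m².

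**Step 5. Is the missing information elsewhere?** The synopsis, section 6.1 and the narrative in 7.4 allow reductions without naming doses. Section 8.3.6.4 speaks of considering whether reductions are appropriate, also without doses. No available section names a reduced dose for the 200 or 150 mg starter, or any daily dose below 150 mg.

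**The case against.** The strongest reply is that nobody would raise the dose. The row is labelled as a reduction, the step is called level -1, the narrative speaks of a lower dose, and the table is a guideline of recommended actions. Reductions are at the investigator's discretion, and the investigator, sponsor and medical monitor can all withdraw a patient at unacceptable risk (sections 6.3.3 and 8.3.6.4). This largely stands. An increase is plainly not intended, and these safeguards lower the risk. They do not tell a site what to give instead: one site could restart at the same dose, another at an undefined lower dose, and a third could stop treatment.

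A second reply is that the group is small. The increase requires a BSA below 1.00 m², a qualifying toxicity, recovery and restart, in a trial mainly of adults. That is plausible but cannot be checked from the documents. The more likely practical problem is the 200 mg tier, where the first step changes nothing. The sponsor did create both lower tiers, so such patients are planned for.

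A third reply is that the mg/m² excess overstates the matter, because the target is approximate and the chart already permits 200 mg/m² at 1.00 m². This is fair as to framing; the +33% does not depend on it.

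A fourth is that requiring a lower restart dose takes away intended discretion. But a lower dose is what the first-reduction row is already meant to produce.

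**Conclusion.** The concern holds. As written, the toxicity table gives a wrong restart dose in two of the three starting-dose tiers: no change at the first step for 200 mg starters, and a 33% increase for 150 mg starters. It contradicts the allowance of two reductions per patient in the same section. This rests on reading the table literally; the surrounding text makes an increase unlikely in practice but leaves the correct dose undefined.

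The number of patients affected is unknown. The documents give neither the share with BSA below 1.40 m² nor the restart rate, so the only bounds are 0 and the planned 29. Sample size, type I error and power are unaffected. It should be fixed, as a matter of dosing safety and consistency between sites.

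**What to change.** In the 7.4 table, replace the single ladder with levels -1 and -2 stated for each starting dose. Counting down from the patient's own starting dose in 50 mg steps would give:

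| Start | Level -1 | Level -2 |
|---|---|---|
| 250 mg | 200 mg (-20%) | 150 mg (-40%) |
| 200 mg | 150 mg (-25%) | 100 mg (-50%) |
| 150 mg | 100 mg (-33%) | 50 mg (-67%) |

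This is arithmetic, not a dose recommendation. Daily doses of 100 and 50 mg appear nowhere in the available text, so the clinical team must set the lowest permitted dose for each tier and say where the patient stops instead.

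Add one sentence: before any permitted 50 mg re-escalation, the restart dose must be lower than the dose at which the toxicity occurred. If a lower tier cannot have two reductions, amend the allowance in the synopsis, 6.1 and 7.4 to match.

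The cost is one table and one sentence in a protocol amendment, plus that matching wording if needed. The 50 mg capsules already supplied allow these steps, and there is no statistical cost.
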